4.5.5 IMP interruptions

The number and percentage of subjects with at least one IMP interruption, the number and percentage of subjects with at least one IMP interruption due to NCFB pulmonary exacerbation and the number of NCFB pulmonary exacerbations which lead to an IMP interruption will be presented.

Moreover, the number of days of IMP interruption overall and due to NCFB pulmonary exacerbations will be summarised using descriptive statistics for continuous variables.

Results will be presented overall and by treatment group for the Safety and mITT Populations.

Notes:

- NCFB pulmonary exacerbations will be linked to the corresponding AE using the AE number collected in the eCRF form “Pulmonary Exacerbation”, i.e. “Please specify corresponding Adverse Event number for this Pulmonary Exacerbation”.
- IMP interruption (days) will be calculated considering stop date and re-start date of IMP as collected in the eCRF “Adverse Event” form using the following formula:

$$\text{IMP interruption (days)} = \text{Re-Start date of IMP} - \text{date of Stop of IMP} + 1.$$
- If any dose with a dose different than “Null” is recorded in the **CCI** logging system during this period, then the **CCI** data will be considered to compute IMP interruption: stop date will be the last IMP dose date before the start of the AE, re-start date will be the first IMP dose date after the start date of the AE.

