9.7. EXACERBATION VISIT/CONTACT

Subjects will be trained by the Investigator to recognise signs and symptoms of NCFB pulmonary exacerbations. At each post-randomisation visit the patient will be reminded about how to recognise symptoms of a NCFB pulmonary exacerbation and instructed to contact the site as soon as they have experienced these symptoms for 24 hours. If feasible, the subject will be asked to attend the clinic at their earliest convenience. If it is not practical for the subject to make an additional clinic visit then relevant information will be collected via phone and the subject will be asked to provide a sputum sample to the clinic in a manner most appropriate to the subject.

Any episodes of pneumonia during the trial should be considered as pulmonary exacerbations and will also require a clinic visit, if feasible. Episodes of pneumonia which are radiologically confirmed and/or requiring intravenous antibiotics and/or hospitalisation will be considered as severe pulmonary exacerbations. Adverse Events of COVID-19 with symptoms of an exacerbation, requiring antibiotics during the course of the study should be considered as pulmonary exacerbations for reporting in the eCRF.

The Investigator will decide if symptoms represent a NCFB pulmonary exacerbation meeting the protocol-defined criteria or not and on the appropriate course of action. It will be clinically determined if the subject requires systemic antibiotic therapy (oral or intravenous) in addition to IMP administration or whether IMP administration should be temporarily interrupted (see below). Treatment of a NCFB pulmonary exacerbation will follow current treatment regimens used in the respective participating trial site.

If the symptoms represent a NCFB pulmonary exacerbation, regardless of whether it meets the protocol definition or not, these should be considered as pulmonary exacerbations for reporting in the eCRF.

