2.1 Primary Endpoint

The primary endpoint of this trial is the mean annual NCFB pulmonary exacerbation rate.

A pulmonary exacerbation is defined as the presence concurrently of at least 3 of the following 8 symptoms/signs for at least 24 hours:

- Increased cough;
- Increased sputum volume and/or consistency;
- Increased sputum purulence;
- New or increased haemoptysis;
- Increased wheezing;
- Increased dyspnoea;
- Increased fatigue/malaise;
- Episodes of fever (temperature $\geq 38^{\circ}\text{C}$);

And it is clinically determined that the subject requires and is prescribed systemic antibiotic therapy.

The start date of a protocol-defined pulmonary exacerbation will be taken as the first day that at least 3 of the pre-defined 8 symptoms/signs occurred concurrently for at least 24 hours, as determined by the Investigator, as documented by the start date of the corresponding AE in the eCRF AE form.

Resolution of a pulmonary exacerbation is defined as the date of completion of the required course(s) of systemic antibiotic treatment and/or the Investigator's judgement that the NCFB pulmonary exacerbation has resolved, as documented by the end date provided for the corresponding AE in the eCRF AE form, whichever is the later of the two dates. The exacerbation end date will be reported at the next scheduled visit or by phone. A new pulmonary exacerbation is only considered to occur if there are at least 14 days between the end of the course of systemic antibiotics and the onset of new qualifying symptoms.

Any episodes of pneumonia during the trial should be considered as pulmonary exacerbations. Episodes of pneumonia which are radiologically confirmed and/or requiring intravenous antibiotics and/or hospitalisation will be considered as severe pulmonary exacerbations. Adverse Events of COVID-19 with symptoms of an exacerbation, requiring antibiotics during the course of the study are considered as pulmonary exacerbations. All pulmonary exacerbations must have the associated

CONFIDENTIAL

Sponsor:	Zambon S.p.A.	Protocol Number:	Z7224L02
----------	---------------	------------------	----------

Pulmonary Exacerbation, Pulmonary Exacerbation Symptoms and Systemic Antibiotic Therapy forms entered into the eCRF, and linked to the corresponding AE.

The treatment of pulmonary exacerbations will follow current treatment regimens used at the respective participating investigational site.

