3.2 Study Treatment

At Visit 2 (within 30 days after Visit 1) eligible subjects with *P. aeruginosa* cultured from their initial sputum sample will be randomised in a 1:1 ratio to receive either colistimethate sodium or placebo.

Subjects will be administered the first dose of the IMP at the investigational site prepared by the site staff and will be instructed by the Investigator or a delegated person how to prepare and self-administer the IMP at home via the CCI Aerosol Delivery CCI system, twice daily (morning and evening) over a period of 12 months. Prior to each administration, a bronchodilator (salbutamol/albuterol) has to be taken.

Colistimethate sodium and placebo will be supplied in 30-vial packs.

Colistimethate sodium is supplied as sterile powder in a glass vial. Each vial contains 1,000,000 International Units (1 MIU) which weighs about 80 mg (equivalent to about 33 mg colistin base activity).

Identical sterile vials for placebo will be used. All vials will be masked with white plastic sleeves so that the contents are not visible. The weight of the powder is insignificant compared to the glass vial.

CONFIDENTIAL

Sponsor:	Zambon S.p.A.	Protocol Number:	Z7224L02
----------	---------------	------------------	----------

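### When the device log contradicts a recorded IMP interruption, the SAP ties the dates to AE onset and can return 3 days both for no gap and for a 14-day gap

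*SAP*

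**What the plan says.** SAP 4.5.5 plans summaries of days of interruption, overall and due to exacerbations, by arm in the Safety and mITT populations.

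- **Default source.** "IMP interruption (days) will be calculated considering stop date and re-start date of IMP as collected in the eCRF" Adverse Event form, with days = re-start minus stop plus 1.
- **Override.** The trigger reads "If any dose with a dose different than “Null” is recorded in the" device log within that period. The log then supplies both dates: "stop date will be the last IMP dose date before the start of the AE", and "re-start date will be the first IMP dose date after the start date of the AE". The formula stays the same.

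Three other provisions matter:

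- IMP is taken "twice daily (morning and evening) over a period of 12 months" (SAP 3.2), so a fully adherent subject has a logged dose on every calendar day.
- The start of an exacerbation is the first day with the required symptoms, "as documented by the start date of the corresponding AE in the eCRF AE form" (SAP 2.1).
- SAP 4.5.1 does not count device records of 12.5% or less as inhaled doses. The override trigger in 4.5.5 excludes only Null records.

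**The concern.** The override exists to correct an eCRF period that the log shows to be wrong. It does so by picking the dosing days on either side of AE onset. It never looks for the days on which dosing stopped, and it has no path to zero when there is no gap. Adding 1 suits a span whose two end days both belong to it, such as a course of antibiotics. Here both end days are days on drug and lie outside the gap.

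A gap that starts after onset is what the protocol would tend to produce. Subjects are told to "contact the site as soon as they have experienced these symptoms for 24 hours" (Protocol 9.7), and the same section allows interruption during systemic antibiotic treatment, without tying it to the onset date. Dosing on the day after onset is therefore plausible.

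At stake is whether the reported days off drug mean what the table titles say, and whether the two arms are described correctly.

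**Working it through.** The documents give no worked figure to reproduce, so the rule is applied literally. Let D be the AE start day, with D = 100.

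**Formulas**

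- Stop = last dose date before D; re-start = first dose date after D.
- Rule: days = re-start − stop + 1.
- Comparison: calendar days with no dose. For one unbroken gap between two dosing days this is re-start − stop − 1, taken at the gap itself.

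**Results once the override applies**

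The 14-day length is an illustration; it equals the initial antibiotic course mentioned in Protocol 10.1.5.

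| Dosing log | Stop | Re-start | Rule | Dose-free days | Error |
|---|---|---|---|---|---|
| Dose every day | 99 | 101 | 3 | 0 | +3 |
| Gap on days 99–112 | 98 | 113 | 16 | 14 | +2 |
| Gap on days 100–113 | 99 | 114 | 16 | 14 | +2 |
| Gap on days 101–114 | 99 | 115 | 17 | 14 | +3 |
| Gap on days 102–115 | 99 | 101 | 3 | 14 | −11 |
| Days 100–113, one dose on 101 | 99 | 101 | 3 | 13 | −10 |
| Days 100–113, one dose on 107 | 99 | 107 | 9 | 13 | −4 |

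Any 14-day gap that starts on D+2 or later gives the same 3 days as the fifth row, because the dose on D+1 is taken as the re-start.

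**Does the reading of before and after matter?** For the subject who missed nothing:

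- day D allowed as stop only: 101 − 100 + 1 = 2;
- day D allowed as re-start only: 100 − 99 + 1 = 2;
- day D allowed as both: 100 − 100 + 1 = 1.

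No reading gives 0.

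**When does the override apply?** The AE form must carry a stop and re-start date, and a non-Null dose must be logged within that period. Take the gap on days 102–115 (last dose 101, next dose 116):

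- If the period includes its end dates, as the plus 1 suggests, the re-start dose on day 116 itself triggers the override. Result: 3.
- If the end dates are excluded and the eCRF dates are accurate, the override does not apply. The eCRF formula gives 116 − 101 + 1 = 16 if stop means the last dosing day, or 116 − 102 + 1 = 15 if it means the first day off drug. The SAP does not say which.
- If the end dates are excluded but the eCRF stop was entered as the onset day, 100, the dose on day 101 triggers the override. Result: 3.

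For the subject with a dose every day, an eCRF stop of 100 and re-start of 102 is enough, since day 101 is dosed.

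**The case against.** The strongest reply is that the rule is narrow. It applies only where a site recorded an interruption and the log contradicts it. A reader might infer that any fully adherent subject is given 3 days. The documents do not support that: without a recorded interruption nothing is calculated. The point that stands is that the rule fails in the very case it was written for.

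Second, the drop from 14 to 3 depends on conditions. With accurate eCRF dates and end dates excluded from the trigger, the override is not used and the result is 15 or 16. With a gap starting by D+1 and no stray dose, it is 16 or 17. This is fair, and the claim is only that the rule can do this. The text does not settle whether end dates count.

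Third, with twice-daily dosing an end date may be a day on which one dose was missed. Counting it could then be defended as a day with any missed dose. That could justify 16 for some 14-day gaps, but not 3 days for a subject who missed nothing.

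Fourth, SAP 4.1.9 says inconsistencies between eCRF and log will be discussed before database lock. That sentence sits under the dates of first and last dose, so it mitigates without changing the derivation in 4.5.5.

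**Conclusion.** The derivation is wrong as written, and the consequence is minor. Once the override applies, a subject with no missed day gets 3 days (1 or 2 on inclusive readings), a 14-day gap starting on D+2 or later gets 3, and a 14-day gap that the rule brackets correctly gets 16. In the cases worked, the error runs from +3 to −11 days. This rests on a dose being logged every day outside the gap and on the strict reading of before and after, except where stated.

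Two stronger readings should be resisted:

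- A reader might infer that every interruption is overstated by at least 2 days. The results above contradict that, because the error can be negative. On the eCRF-only route the excess is 1 or 2 days, depending on what the stop date means.
- A reader might multiply a fixed excess by the planning exacerbation rates to obtain a spurious difference between arms. The documents do not support this. Protocol 9.7 leaves interruption to the Investigator's judgement, no excess is fixed, and how often the override would apply is unknown.

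The rule feeds only Tables 14.1.13.1 and 14.1.13.2, which are descriptive. Exposure time and the offset (SAP 4.1.7, 4.7.4), exposure days and extent of exposure (4.5.2, 4.5.3), adherence (4.5.4) and the adherence criterion for the PP population (3.5.4) use other definitions. No efficacy result depends on it.

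**What to change.** Amend 4.5.5 as follows. This concerns the calculation only, not when treatment should be interrupted.

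- **Trigger.** Use the inhaled-dose definition of 4.5.1, so that a record of 12.5% or less does not set off the override. State whether the end dates belong to the period.
- **Locating the gap.** When the log contradicts the eCRF period, find the dose-free gap or gaps in the log that overlap that period. Follow them beyond the period or the AE dates if they extend further. Searching only from AE start to AE end could cut gaps short and could count ordinary missed days as interruptions.
- **Counting.** Count calendar days with no inhaled dose, which is re-start − stop − 1 for each gap between two dosing days. Allow zero. For days 102–115 this gives 116 − 101 − 1 = 14; for the subject with a dose every day it gives 0. Also state whether a recorded interruption that resolves to zero still counts as an interruption in the subject counts.
- **eCRF dates only.** State whether stop is the last dosing day (then re-start − stop − 1) or the first day off drug (then re-start − stop).

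The cost is one derivation and its wording. SAP 4.5.1 expects the device data to be complete, so no new data are needed.

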4.6 Prior and Concomitant Medication

The incidence of prior and concomitant medications will be presented by therapeutic area according to the Anatomical Therapeutic Chemical (ATC) level 4 classification and preferred drug name, by treatment and overall for the mITT Population.

Prior medications are those that started and stopped before exposure to IMP; concomitant medications are all medications taken during the study period, including those started before but on going at first IMP dose.

Where a medication start/stop date is partially or fully missing, and it is unclear as to whether the medication is prior or concomitant, it will be assumed that it is concomitant.

Notes:

CONFIDENTIAL

Sponsor:	Zambon S.p.A.	Protocol Number:	Z7224L02
----------	---------------	------------------	----------

- Prior and concomitant medications are all medications collected in the eCRF forms Prior and Concomitant Medications and Systemic Antibiotic Therapy.
- Medications are coded using the World Health Organisation (WHO) Drug Dictionary, WHO-DD (please refer to the final Data Management Plan for the latest coding information);
- Only the number of subjects with medications (not the number of medications) will be presented;
- If a subject has multiple occurrences of a medication, the subject will be presented only once in the respective subject count;
- Prior and concomitant medications will be summarised in separate tables;
- Medications will be displayed in descending ATC text and drug name frequency overall and then alphabetically.

4.7 Efficacy / Primary and Secondary Analysis

The analysis of the trial is on a comparative basis. For all efficacy parameters, summaries will be presented by treatment group and comparisons will be made between colistimethate sodium versus placebo. Two-sided p-values <0.05 will be considered statistically significant and 95% two-sided CIs will be presented, where appropriate.

Primary and secondary efficacy variables, where not stated differently, will be summarised for the mITT and, where relevant, PP Populations. The primary analysis will be performed on the mITT Population. Analyses conducted using the PP will be considered supportive.

The health economic variables will be analysed on the mITT Population only.

4.7.1 Primary Endpoint

The primary endpoint of this trial is the annual NCFB pulmonary exacerbation rate.

The analysis of this endpoint requires for each subject both their count of NCFB pulmonary exacerbations and their exposure to randomised treatment. NCFB pulmonary exacerbations are defined in Section 4.7.4 and follow-up time is computed as detailed in Section 4.1.7.

4.7.2 Normality Assumption Checking

Not applicable.

4.7.3 Closed Testing Procedure for Primary Analysis

Not applicable.

4.7.4 Method of Analysis for Primary Endpoint

The NCFB pulmonary exacerbations collected from the Pulmonary Exacerbation eCRF form will be considered for the analysis. All cases in which the variable “Do these symptoms meet the protocol-defined criteria for NCFB pulmonary exacerbation?” is not consistent with data collected in the corresponding eCRF Pulmonary Exacerbations Symptoms form will be

CONFIDENTIAL

Sponsor:	Zambon S.p.A.	Protocol Number:	Z7224L02
----------	---------------	------------------	----------

discussed during the blind review meeting. The decisions taken will be documented in the Blind Data Review and Analysis Sets Report.

The start of a protocol-defined NCFB pulmonary exacerbation will be taken as the first day that at least 3 of the 8 defining symptoms occurred concurrently for at least 24 hours as determined by the Investigator, as documented by the start date of the corresponding AE in the eCRF Adverse Events form and reviewed, where necessary, by the DAC (see Section 4.2.1) taking into consideration aspects such as start/stop date and associated systemic antibiotic therapy/hospitalisations.

Only NCFB pulmonary exacerbations with start date \geq date of first IMP dose and \leq date of treatment completion/discontinuation will be considered in the analysis. NCFB pulmonary exacerbations with start date = date of first IMP dose will be discussed on a case-by-case basis during the blind review of the data in order to evaluate whether they should be classified as having occurred in the screening period. The decisions taken will be documented in the Blind Data Review and Analysis Sets Report.

Resolution of a NCFB pulmonary exacerbation is defined as the date of completion of the required course(s) of antibiotic treatment, as collected in the eCRF Systemic Antibiotic Therapy form, and/or the Investigator's judgement that the NCFB pulmonary exacerbation has resolved, as documented by the end date provided for the corresponding AE in the eCRF Adverse Events form, whichever is the later of the two dates. If more than one systemic antibiotic therapy is administered for a NCFB pulmonary exacerbation, then the latest end date will be considered as the date of completion of the required course of antibiotic treatment.

In the case of a partial onset date of NCFB pulmonary exacerbation due to missing day, the onset of the event will be assumed to be the first day of the month. If the resultant derived date is prior to the date of first IMP dose, then it will be assumed to be equal to the first IMP dose date. Resultant derived dates will be reviewed during the blind review meeting and documented in the Blind Data Review and Analysis Sets Report.

In case of a partial resolution date of NCFB pulmonary exacerbation due to missing day, the resolution of the event will be assumed to be the last day of the month. If the resultant derived date is after the treatment completion/discontinuation date, then it will be assumed to be equal to the treatment completion/discontinuation date.

In case a NCFB pulmonary exacerbation presents a symptom with missing duration, following a conservative approach, the longest duration based on the start and stop dates of that symptom and until the resolution date of the NCFB pulmonary exacerbation will be imputed.

Two NCFB pulmonary exacerbations will be considered as a single episode in the statistical analysis if the second exacerbation started less than 14 days after the end of the systemic antibiotic therapy for the previous exacerbation (start date of the exacerbation - end date of the treatment of the previous exacerbation $<$ 14 days). In case of more than two exacerbations for the same subject, this rule will be applied iteratively (therefore, more than two exacerbations may be considered as a single episode). Such cases will be discussed during the blind review of the data and the decisions taken will be documented in the Blind Data Review and Analysis Sets Report.

The above rule will not apply to the analysis of NCFB pulmonary exacerbations as AEs in the safety analysis.

In case of NCFB pulmonary exacerbations considered as a single episode:

CONFIDENTIAL

Sponsor:	Zambon S.p.A.	Protocol Number:	Z7224L02
----------	---------------	------------------	----------

- the start date of the first event will be considered as the start date;
- the stop date of the last event will be considered as the stop date;
- a worst case approach will be considered for duration of symptoms and requirement of hospitalisation. For example, if one of two exacerbations considered as a single episode has/have increased dyspnoea for ≥ 24 hours and < 48 hours and the other one has increased dyspnoea for ≥ 48 hours, the single episode will be considered in the analysis as having dyspnoea for ≥ 48 hours.

In order to investigate whether the use of inhaled colistimethate sodium reduces the frequency of pulmonary exacerbations compared to placebo in subjects with NCFB chronically infected with *P. aeruginosa*, the following hypothesis will be tested:

- Null hypothesis: there is no difference between inhaled colistimethate sodium and placebo as regards the effect on the pulmonary exacerbation rate
- Alternative hypothesis: inhaled colistimethate sodium reduces the pulmonary exacerbation rate in favour of inhaled colistimethate sodium compared to placebo.

The null hypothesis must be rejected for the efficacy of inhaled colistimethate sodium to be considered demonstrated.

The number and the percentage of subjects with NCFB pulmonary exacerbations, the number of NCFB pulmonary exacerbations and the total follow-up time in years, as defined in Section 4.1.7, will be summarised by treatment group.

The number of NCFB pulmonary exacerbations during the treatment period will be analysed using a negative binomial model including treatment, country, as detailed in Section 4.9.1, and use of stable concomitant therapy with oral macrolides as fixed effects and log-exposure time on treatment as an offset. The log-time on treatment in years will be calculated as $\ln(\text{exposure time})$.

The adjusted mean annual NCFB pulmonary exacerbation rates in each treatment group and the adjusted rate ratio with their 95% CIs will be estimated by the model. OBSMARGINS option will be used for the estimates. The number of subjects considered in the model will be provided by treatment group.

The number and the percentage of subjects with 0, 1, 2 or >2 pulmonary exacerbations will be presented.

The number and the percentage of subjects with pulmonary exacerbations, the number of pulmonary exacerbations will also be presented by treatment group for severe (defined as those requiring intravenous antibiotics and/or hospitalisation) and not severe exacerbations.

A simple summary of the annualised pulmonary exacerbation rate will be calculated across subjects for each treatment as $\{\sum_i^{n_j} \text{exacerbation}_i / \sum_i^{n_j} \text{exposure}_i\}$ where j denotes randomised treatment group, $i = 1 \dots n_j$ denotes the number of subjects, exacerbation_i and exposure_i denote the number of exacerbations and exposure time for subject i .

The total duration of systemic antibiotic therapy, overall and by route, will be summarised by treatment group using descriptive statistics for continuous variables as well as distribution frequencies for the following categorisations:

- 1-7 days;

CONFIDENTIAL

Sponsor:	Zambon S.p.A.	Protocol Number:	Z7224L02
----------	---------------	------------------	----------

- 8-15 days;
- 16-30 days;
- >30 days;
- Not Evaluable.

The total duration of systemic antibiotic therapy will be summarised overall and by category.

The duration of systemic antibiotic therapy will be evaluated considering the start and end date of the therapy associated with the pulmonary exacerbation. The duration of each course of systemic antibiotic therapy will be calculated using the following formula:

- Duration (days) = stop date – start date +1

For exacerbations treated with more than one systemic treatment, the duration will be calculated by summing the duration of the associated treatments. The overlapping days will be counted only once.

It is expected that all systemic antibiotic therapy will have completed (i.e. will have a stop date) at the end of the study when data are final, as all therapy stop dates are required to be known in order to derive the resolution date of pulmonary exacerbations per the definition described earlier in this section.

In order to calculate the duration of each course of systemic antibiotic therapy, the following rules will be applied for partial dates of start and stop date of systemic antibiotic therapies:

For the start date:

- if only the day is missing, the first day of the month will be assumed. If the resulting derived date is prior to the start date of the exacerbation, then start date of therapy will be assumed to be equal to the start date of the pulmonary exacerbation.
- if the day and the month are missing, then the date will not be imputed and the duration will be classified as “Not Evaluable”.

For the stop date:

- if only the day is missing, the last day of the month will be assumed;
- if the day and the month are missing, then the date will not be imputed and the duration will be classified as “Not Evaluable”.

Resultant dates will be discussed during the blind review meeting and documented in the Blind Data Review and Analysis Sets Report.

The above summary/analysis will be performed using the mITT Population and, where appropriate, the PP Population. Results for the PP Population will be considered as supportive.

4.7.4.1 **CCI** Analysis Using Alternative Definition of NCFB Pulmonary Exacerbation

A **CCI** analysis will be conducted using an alternative definition of NCFB pulmonary exacerbation for the mITT Population. The re-classification of pulmonary exacerbations will

CONFIDENTIAL

Sponsor:	Zambon S.p.A.	Protocol Number:	Z7224L02
----------	---------------	------------------	----------

be done during the blind review meeting and documented in the Blind Data Review and Analysis Set Report.

In this CCI analysis, a NCFB pulmonary exacerbation is defined as deterioration in three or more of the following key symptoms for at least 48 hours:

- [REDACTED]
- [REDACTED]
- [REDACTED]
- [REDACTED]
- [REDACTED]
- [REDACTED]

And:

CCI [REDACTED]
[REDACTED]
[REDACTED]

Subjects experiencing NCFB pulmonary exacerbations according to this alternative definition will be identified as those subjects having:

- An AE on the eCRF Adverse Events form with a MedDRA coded Preferred Term of “infective exacerbation of bronchiectasis” that is at least 48 hours in duration (i.e. stop date of AE – start date of AE + 1 ≥ 2);
- At least 3 of the above symptoms on the eCRF Pulmonary Exacerbation Symptoms form for the Pulmonary Exacerbation Number corresponding to that AE, where those symptoms all occur between the start and stop dates of the AE;
- At least 1 therapy on the eCRF Systemic Antibiotic Therapy form for the Pulmonary Exacerbation Number corresponding to that AE.

Analysis will be conducted following the same rules and methods as detailed above for the main definition of NCFB pulmonary exacerbations.

